Exploratory aims will examine the influence of the following on weight loss at 6 mos.: behavioral session attendance, compliance with the recommendations for diet (energy intake, number of meals/shakes, servings of fruits/vegetables), PA (min of moderate-vigorous PA, min sedentary time), self-monitoring of diet and PA, sleep, and medications assessed over the time period of interest, i.e. (0-6 and 0-18 mos.) and the change in self-efficacy for PA and dietary change, dietary self-regulation, social support for diet/PA, and barriers to PA from 0-6 mos. We will examine the influence of these factors as covariates, in addition to treatment, on weight loss at 6 mos. As we have 128 observations with a rule of thumb of at least 30 observations for each variable in the model, judicious model selection will be completed as we can only expect to identify ~ 4 variables that are related to weight loss in a single model. First, we will assess if these variables differ by treatment at the 0.10 level and if they do they will be considered for future modeling. If in a two-factor model, the variable and treatment have a potential interaction at the 0.10 level that interaction will be considered for future modeling. Subsequently, the main effects and interaction effects along with treatment will be examined in a joint model. Given the pitfalls of forward and backward selection, we will utilize best subsets criteria based upon Mallow's Cp statistic to produce the most parsimonious and least biased model of weight loss at 6 months. This should allow us to identify what variables most highly influence our outcome along with treatment and/or the mechanism(s) of action that are impacting weight loss. We will do the same for weight loss at 18 months, as this measure may have similar or different variables that impact this long-term outcome.

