Missing Data/ imputation. All analyses will be based on intent-to-treat principles and missing data for analyses of the primary aim will be imputed; therefore, oversampling for attrition is not needed. We will determine if the proportion of participants lost to follow-up differs by treatment. If so, we will determine if there are differences in demographic characteristics (sex, age, baseline weight, $p < 0.05$) between completers and those lost to follow-up. If missing data are related to treatment and/or these demographic characteristics, we will use model based multiple imputation; otherwise, we will use traditional multiple imputation. Statistical analysis will be completed with SAS version 9.4 or higher.

REFERENCES

2. Brault MW. Americans with Disabilities: 2010 Current Population Reports. Washington, DC: US Census Bureau; 2012. p. 40-131.

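### Best-subsets selection by Mallows' Cp does not cure the faults of stepwise selection, and with the plan's 0.10 screens it can often keep noise terms; the limit of about four variables also assumes all 128 participants are complete

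*Combined protocol and SAP*

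**What the plan says.** The Exploratory aims paragraph, under Sample Size, Statistical Methods, and Power Calculation, lists process variables and questionnaire change scores that may relate to weight loss. It then sets out a sequence:

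- **Size limit.** "As we have 128 observations with a rule of thumb of at least 30 observations for each variable in the model", so "we can only expect to identify ~ 4 variables that are related to weight loss in a single model".
- **Main-effect screen.** "we will assess if these variables differ by treatment at the 0.10 level and if they do they will be considered for future modeling".
- **Interaction screen.** If, in a two-factor model, "the variable and treatment have a potential interaction at the 0.10 level that interaction will be considered for future modeling".
- **Selection.** "Given the pitfalls of forward and backward selection, we will utilize best subsets criteria" using Mallows' Cp, "to produce the most parsimonious and least biased model of weight loss at 6 months".
- **Use of the result.** "This should allow us to identify what variables most highly influence our outcome along with treatment and/or the mechanism(s) of action".

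The same is to be done at 18 months. The paragraph gives no resampling, shrinkage, validation or multiplicity step, and no handling of missing process variables. The Missing Data/imputation paragraph puts all analyses on intent-to-treat principles but says only that "missing data for analyses of the primary aim will be imputed".

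**The concern.** The plan recognises that stepwise selection has problems and offers best subsets as the way round them. The main problem is shared: the same data pick the terms and then estimate them. Terms survive partly because their estimates happened to be large, so retained coefficients are biased away from zero on average, and any ordinary standard error ignores the search. Cp is also a lenient criterion, which sits badly with a claim of parsimony.

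What is at stake is how the exploratory results are read. A variable retained by chance could be reported as one that strongly influences weight loss, or as a mechanism, with nothing in the plan to show how stable that selection is. Separately, the size limit is worked out from the full randomised number, although the plan does not say these analyses will have that many complete records.

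**Working it through.** **1. The plan's own figures.** 64 per group gives 2 × 64 = 128, and 128/30 = 4.27, so about four variables reproduces.

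**2. How lenient Cp is.** Take the model with the lowest Cp (the plan does not state the exact rule). Adding one variable lowers Cp when its F exceeds about 2. For a variable with no effect, P(chi-square, 1 df > 2) = 0.157, about three times the rate of a 0.05 test. For k independent null variables sent straight to Cp, P(at least one kept) = 1 − (1 − 0.157)^k: 0.50 for k = 4, 0.64 for k = 6 and 0.82 for k = 10.

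**3. The plan's sequence.** The plan screens before Cp, so step 2 alone does not describe it. The documents give no candidate count; the list can be read as about 14 to 17.

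Take 15 null candidates with no arm differences and no interactions. About 15 × 0.10 = 1.5 pass the main-effect screen, and P(at least one kept) = 1 − (1 − 0.10 × 0.157)^15 = 0.21.

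Interactions behave differently because their screen uses the outcome. Passing at 0.10 needs |t| above about 1.66, so F above about 2.7. That already exceeds Cp's threshold of 2, so most interactions that pass are kept.

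Two sets of simulations ran the full sequence at N = 128 with all candidates null. Set A used 15 candidates with correlation 0.2. Set B used 16 candidates, independent or with correlation 0.3, a 3 kg treatment effect, SD 6 kg, treatment forced in and a cap of four terms. In set B, arm-differing candidates differed by 0.5 SD.

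| Setting | Set A, P(≥1 noise term) | Set B, P(≥1 noise term) |
|---|---|---|
| No arm differences, no interactions | 17% | 22% |
| Interactions, no arm differences | 60% | 78–85% |
| 8 candidates differ by arm, no interactions | 67% | 72% |
| Both | 93% | 92–96% |

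The sets agree except in the second row, so that row is best read as a majority of trials rather than an exact value. With three true predictors among the 16, set B kept at least one noise term in 79–89% of trials.

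**4. Comparison with stepwise.** On set B's candidates in the two settings with interactions, forward or backward selection at p < 0.05 kept noise in 52–74% of trials, against 78–96% for Cp. The 0.05 threshold is an assumption, since the plan names none. A BIC penalty lowered the figure to 38–56%, so a stricter criterion helps but does not remove the problem.

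**5. Effect of N.** With independent candidates, interactions and no arm differences, set B gave 0.85 at N = 128 (cap four) and 0.85 at N = 102 (cap three). With both features it gave 0.96 and 0.94. Sample size in this range makes little difference.

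**6. Size limit on complete records.** Limit = 128 × (1 − attrition)/30.

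| Attrition | Complete records | Limit |
|---|---|---|
| 0% | 128 | 4.27 |
| 6.25% | 120 | 4.00 |
| 10% | 115.2 | 3.84 |
| 20% (the plan's completer scenario) | 102.4 | 3.41 |
| 30% (assumed) | 89.6 | 2.99 |

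Four variables at 30 each need 120 complete records. The plan expects more loss over time, so the 18-month limit is lower than the 6-month one, but the plan gives no figure.

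**The case against.** Several counter-arguments have force.

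- **The screens restrict what reaches Cp.** A reader might infer that Cp alone keeps noise in nine trials out of ten. That follows only if all candidates go straight to Cp, which the plan does not do. With no arm differences and no interactions the figure is about 17%. This stands, and the cause is the screens and Cp acting together. However, the plan admits interactions, and the arms differ by design in exercise delivery and self-monitoring, so the most favourable row is not the natural one.
- **All-null candidates are an extreme case.** Attendance, energy intake and activity plausibly relate to weight loss. This stands, but adding true predictors did not remove the noise.
- **Treatment might be dropped.** A reader might infer this from an unrestricted search. The paragraph repeatedly speaks of treatment alongside the other variables, so the documents do not support it. Stating that treatment is forced in is only a clarification.
- **The trial will not have 128 observations.** This is too strong. The power paragraph uses 20% as a scenario and expects less. The fair point is that complete data are assumed without a basis, and that the intent-to-treat sentence leaves imputation for these variables unclear. A move from 4.3 to 3.4 in a rule of thumb is small.
- **The bias claim can be read in Cp's own sense,** as low bias from omitted terms, and the plan promises no p-values from the selected model. Both are fair. Neither supports inferring mechanisms from the result.
- **Noise variables would shape the next intervention.** The documents do not say so; the Study Type and Design section gives that purpose to structured interviews.

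**Conclusion.** The point holds in a limited form. Best subsets by Cp does not avoid selection bias, admits a null variable about 15.7% of the time, and is followed by no check of stability or optimism before variables are called influential or mechanistic. Under the plan's sequence the chance of at least one noise term runs from roughly 17% to over 90%. It is about 60% to 70% when either interactions or eight arm-differing candidates are present, and up to 85% for interactions if candidates are independent. These figures assume about 15 or 16 mostly null candidates, selection by lowest Cp and modest or no correlation; the plan settles none of these.

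The size limit falls from 4.3 to 3.4 at 20% attrition. That is a minor correction at 6 months and more relevant at 18.

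Severity is low. The aims are labelled exploratory, and the primary and secondary comparisons do not depend on this model.

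**What to change.** - State that treatment is forced into every model and that any interaction keeps its main effect.
- Repeat the whole sequence, both screens and the Cp step, in bootstrap samples. Report each term's inclusion frequency and shrunken (optimism-corrected) coefficients. The number of samples and any frequency threshold are the team's choice, but should be set in advance.
- Give no unadjusted p-values from the selected model.
- Remove the claim of least bias, and describe selected variables as hypothesis-generating rather than as mechanisms.
- State how missing process variables are handled, and base the size limit on the complete observations available: about three variables at 20% attrition, fewer at 18 months if loss is greater. Say whether treatment counts towards the limit.

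The cost is programming time, and fewer variables will be declared influential. No new data are needed.

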We propose a 2-arm randomized trial (group remote (*GR*) vs. individual home visit (*IH*)) using intent-to-treat principles, to compare body weight following weight loss (6 mos.) and maintenance (18 mos.) in overweight/obese adults with MRDs. interventions will be delivered by trained health educators and will include behavioral sessions, a reduced energy diet (eSLD), increased PA, and self-monitoring of weight using electronic scales. The *GR* arm will be delivered via video conferencing (Zoom™ software) on a tablet computer (iPad mini) with self-monitoring of diet and PA using commercially available technologies. Participants in the *IH* arm will self-monitor diet and PA using paper and pencil records. Due to COVID-19, all Cohort 1 *IH* intervention meetings will be held by phone per CDC social distancing recommendations. Participants are asked to send pictures of the tracking sheets to the health educator prior to the phone meeting. The primary outcome (weight) will be assessed during home visits at baseline (mo. 0), following weight loss (6 mos.), during (12 mos.) and at the end of maintenance (18 mos.). Our group has experience with all proposed intervention components and outcome assessments from previously completed (44, 58, 71, 78, 88, 89) or on-going trials (DK83589, HD79642). The following design attributes, described in detail subsequently, ensure the scientific rigor of the proposed trial: 1) Randomized design with equal allocation to groups, with allocation assignment concealed. 2) Adequate statistical power to address the primary aim. 3) Strategies to ensure the recruitment of sufficient participants to achieve our desired sample size. 4) Retention/incentive strategies to reduce loss to follow-up. 5) Controlling for attention by maintaining equal contact in both groups. 6) Secondary/exploratory aims to maximize the use of data, e.g., analysis to examine the impact of process variables/participant characteristics on

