Energy Expenditure of Remote Exercise Sessions (optional). Energy expenditure of the remote sessions will be assessed in a volunteer sample using a previously validated portable, open-circuit indirect calorimeter (Cosmed, Italy) which measures breath-by-breath ventilation, expired oxygen, and carbon dioxide. The flow turbine will be calibrated using a 3.0-L syringe. The lightweight (~1.5 kg) portable system will be attached by a harness around the waist and shoulders of the participant before each assessment. During exercise sessions, participants will breathe into a facemask that directs air into the unit housing the O₂ and CO₂ analyzers. Data will be retrieved for analysis via a serial port interface and software provided with the calorimeter, and aggregated over 20-second epochs for the calculation of 1-min averages. MET levels will be age corrected using the Schofield equation (88) as recommended by McMurray et al (89). Participants will be asked to wear wrist ActiGraphs during the assessment for comparison of physical activity levels between devices.

SAMPLE SIZE, STATISTICAL METHODS, AND POWER CALCULATION

Power/sample size. The mean 6 mo. weight loss in our completed trial in adults with MRDs, using a protocol similar to the *IH* arm in the proposed trial, i.e., eSLD and behavioral counseling delivered by monthly home visits, was 5.5 kg (58). This does not reach the 8.5 kg (~5%) average 6 mo. weight loss defined as clinically meaningful by current weight management guidelines (53). We expect 6 mo. weight loss in the *GR* arm, which includes weekly group counseling and group exercise, will reach or exceed 8.5 kg. To detect a clinically meaningful difference of 3 kg (133, 176-180) in 6 mos. weight loss between the *IH* and *GR* arms, with 80% power and a type 1 error rate of 0.05, assuming a common standard deviation of 6 kg, will require 64 participants/group. Secondarily, we will have 70% power to detect a 3 kg difference in a completer analysis with an attrition rate of 20%; however, we expect attrition will be lower based on experience (71, 78, 181), and our use of retention/incentive strategies to minimize loss to follow-up. Thus, a sample of 64/group will provide adequate power for both our primary intent-to-treat analysis with imputed missing data (power = 80%) and our secondary completer only analysis (70%).

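### The primary imputation method is chosen by a weak test of differential dropout, the follow-on check of baseline predictors cannot alter that choice, and neither imputation model is defined

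*Combined protocol and SAP*

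**What the plan says.** The paragraph on missing data and imputation closes the section on sample size, statistical methods and power. It states that missing data for the primary aim will be imputed and, on that ground, does not enlarge the sample for attrition. The method is then picked in steps:

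1. "We will determine if the proportion of participants lost to follow-up differs by treatment". No test or significance level is given.
2. "If so, we will determine if there are differences in demographic characteristics", namely sex, age and baseline weight, between completers and those lost, at p < 0.05.
3. If missingness is related to treatment, to those characteristics, or to both, *model based* multiple imputation is used; "otherwise, we will use traditional multiple imputation".

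Neither method is defined and no variables are listed for either.

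The primary analysis (Analysis plans) is an unadjusted two-sample t-test of 6-month weight loss, run by intent to treat and in completers. The sample size paragraph aims "To detect a clinically meaningful difference of 3 kg" "with 80% power and a type 1 error rate of 0.05"; "assuming a common standard deviation of 6 kg, will require 64 participants/group". It allows for 20% attrition overall and gives no rates by arm.

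**The concern.** A missing-data model should contain whatever plausibly predicts both the outcome and its absence, whether or not a test on this sample reaches significance. Here the model is settled after the data are seen, by a test that was not sized for the purpose. The check on baseline predictors is also nested inside the arm comparison, so it runs only when it is no longer needed for the decision.

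The stakes are higher than usual because the plan relies on imputation in place of extra recruitment, and the primary t-test has no covariates. Any arm or baseline information must therefore enter through the imputation model. Differential loss is plausible: one arm meets by group video and the other by individual visits (by phone for Cohort 1). The plan itself lists age, sex, baseline weight, type of disability and wheelchair use as characteristics that may affect weight change.

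**Working it through.** **Inputs from the documents.** 64 per arm ("As we have 128 observations" in total; "Randomized design with equal allocation to groups"), difference 3 kg, SD 6 kg, alpha 0.05, attrition 20% overall.

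**Assumptions.** Pretest alpha 0.05 two-sided; the per-arm loss rates; correlation of baseline weight with weight loss 0.3 to 0.5; dropout log-odds rising 0.7 per SD of baseline weight.

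**1. The plan's own figures.** Noncentrality = 3 / (6 × √(2/64)) = 2.83, which gives 80.1% power (two-sided t, 126 df). With 20% loss, 0.8 × 64 ≈ 51 per arm: 3 / (6 × √(2/51)) = 2.52, giving 70.6%. The stated 80% and 70% are reproduced.

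**2. Power of the pretest.** With p̄ the mean of the two loss rates,

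z = [|p1 − p2|√n − 1.96√(2p̄(1 − p̄))] / √[p1(1 − p1) + p2(1 − p2)], power ≈ Φ(z).

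For 15% against 25%: (0.10 × 8 − 1.96 × 0.566) / 0.561 = −0.55, so 29%. Exact enumeration of the chi-square test at 64 per arm:

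| Loss by arm | Pretest significant |
|---|---|
| 20% vs 20% | 5% |
| 17.5% vs 22.5% | 11% |
| 15% vs 25% | 29% |
| 12% vs 28% | 63% |
| 10% vs 30% | 82% |

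Fisher's test is weaker (22% at 15% vs 25%; 77% at 10% vs 30%). Reaching 80% power at 15% vs 25% would take 250 per arm.

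**3. What the rule can produce.**

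| Arm test | Demographic check | Method |
|---|---|---|
| Significant | Significant | Model based |
| Significant | Not significant | Model based, because of arm alone |
| Not significant | Not done | Traditional |

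The middle column never changes the right-hand one. If heavier participants drop out equally often in both arms, the arm test is significant only about 5% of the time, so baseline weight goes unexamined about 95% of the time. In simulations of that case, the weight comparison would have been significant, had it been run, in about 81% of trials where the arm test was not.

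**4. If the default omits arm.** Missing values in both arms are drawn toward one pooled mean, so with equal loss the expected difference is (1 − 0.20) × 3 = 2.4 kg. Simulation over balanced and imbalanced loss gave about 2.4 to 2.6 kg. With proper multiple imputation at 20% missing at random (1,500 trials per model), power was 52% without arm and 70% with it.

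**5. If the default includes arm but omits baseline weight.** Each arm is filled from its own completers, so the estimate is in effect the completer difference, and

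bias = SD × correlation × (difference between arms in mean standardized baseline weight among completers).

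| Loss, GR vs IH | Difference in completers' mean weight (SD) | Bias at correlation 0.3 to 0.5 |
|---|---|---|
| 20% vs 20% | 0 | 0 |
| 15% vs 25% | 0.063 | 6 × 0.3 × 0.063 = 0.11 to 6 × 0.5 × 0.063 = 0.19 kg |
| about 11% vs 30% | 0.120 | 0.22 to 0.36 kg |

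Simulation (4,000 runs per scenario) agrees: 2.97 to 3.01 kg when balanced, 3.13 to 3.20 kg and 3.21 to 3.36 kg when imbalanced. The sign reverses if the heavier loss is in GR. A model with both arm and baseline weight gave 2.97 to 3.02 kg throughout.

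**The case against.** The strongest reply is that nothing in the text says the default branch leaves anything out. *Traditional* multiple imputation is undefined and could contain arm and every baseline variable. That stands. A reader might infer that predictors of dropout will usually be omitted, but the documents show only that the content is unspecified and the choice data-driven. Nor is imbalance usually missed at every size: gaps of about 16 points or more are detected more often than not, and the larger biases in step 5 belong to gaps at which the pretest would mostly have selected the other branch.

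A reader might also infer that balanced, weight-related dropout distorts the treatment comparison. It barely does so if arm is in the model. Nor is there evidence of false-positive inflation from the selection step: in null simulations of the pretest procedure, type I error was 4.5% to 5.4% with arm in the default and 1.4% to 2.8% without it.

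The plan also has a completer analysis and, for 0 to 18 months, a mixed model with arm and baseline weight and no pretest. These could expose a discrepancy, but they do not replace the primary imputed analysis. Finally, the nested wording may be a drafting slip, with the demographic check meant to stand alone. If so, the text still needs correcting, and the method would still be chosen by significance tests.

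**Conclusion.** The point holds as a flaw in the stated decision rule. The method for the primary analysis depends on a pretest that misses a 10-point gap in loss about 71% of the time; the second check has no effect on the outcome; and neither candidate model is specified. The consequences are conditional. Omitting arm would cost about 0.6 kg of a 3 kg difference at 20% missing. Omitting baseline weight would bias the estimate by roughly 0.2 to 0.3 kg (0.1 to 0.4 kg across the cases run), and only when loss is both weight-related and imbalanced. These sizes rest on the assumed pretest alpha, per-arm loss rates, weight correlation and dropout slope, none of which the documents give. The stronger conclusion, that the primary result will be biased, is not supported. The sponsor should still make the change, since a fixed model avoids these risks at almost no cost.

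**What to change.** Delete both pretests and prespecify one multiple imputation model, used whatever the pattern of loss. It should always include arm, baseline weight, age, sex, a small set of other baseline variables already collected (wheelchair use, for example) and the observed staff-measured weights at 6, 12 and 18 months. With about 51 completers per arm expected at 20% loss, keep the list short; including arm as a term is enough, and imputing separately by arm is optional. Home electronic-scale weights could be added only if they are stored for analysis, which the documents do not say.

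Add a delta-shift sensitivity analysis in which imputed weight losses are made progressively less favorable, including by different amounts in the two arms, to show how far the conclusion depends on data being missing at random. Comparisons of dropout by arm and by baseline characteristics can stay as descriptive reporting.

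The cost is SAP wording and minor code, with no new data collection.
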